9.2. Liver Chemistry Monitoring Criteria

For subjects with ALT ≥ 3 X ULN **but** < 5 X ULN **and** bilirubin < 2 X ULN, without symptoms indicative of hepatitis or rash, and who can be monitored safety for 4 weeks, the following actions should be taken:

- Notify the GSK Medical Monitor within 24 hours of learning of the abnormality to discuss subject safety
- Continue administration of study drug
- Evaluate liver chemistries (ALT, AST, alkaline phosphatase, bilirubin) weekly until they resolve, stabilize or return to within baseline levels
- If at any time the subject meets any of the liver chemistry stopping criteria 1 to 5 (Section 3.9.1), then proceed as described in Section 9)
- If, after 4 weeks of monitoring, ALT < 3 X ULN and bilirubin < 2 X ULN, then monitor subjects twice monthly until liver chemistries normalize or return to within baseline values

9.3. Drug Restart/Rechallenge Following Liver Events that are Possibly Related to Study Drug

Approval by the GSK Medical Monitor to restart/rechallenge study drug may be considered where:

- The subject is receiving compelling benefit, the benefit exceeds the risk, and no effective alternative therapy is available. Approval of restart/rechallenge by the Institutional Review Board (IRB) or Independent Ethics Committee (IEC) must be obtained, as required

- If the restart/rechallenge is approved by GSK in writing, then the subject must be provided with a clear description of the possible benefits and risks of administration of study drug, including the possibility of a recurrence, a more severe liver injury or death.
- The subject must also provide signed informed consent specifically for the study drug restart/rechallenge. Documentation of the informed consent must be recorded in the subject's study chart.
- Study drug must be administered at the dose specified by the GSK Medical Monitor.
- Subjects approved by GSK for restart/rechallenge of study drug must return to the clinic twice a week for evaluation of liver chemistry tests until stable liver chemistries have been demonstrated and laboratory monitoring may resume per protocol.

9.4. Drug Restart Following Transient, Resolving Liver Events Not Related to Study Drug

Approval by the GSK Medical Monitor to restart study drug(s) may be considered where:

- Liver chemistry abnormalities have a clear underlying cause (e.g., biliary obstruction, hypotension) and liver chemistries have improved to normal or are within 1.5 X baseline and ALT <3X ULN. Approval of restart by the Institutional Review Board (IRB) or Independent Ethics Committee (IEC) may be required.
- If the restart/rechallenge is approved by GSK in writing, then the subject must be provided with a clear description of the possible benefits and risks of administration of study drug(s), including the possibility of a recurrence, a more severe liver injury or death.
- The subject must also provide signed informed consent specifically for the study drug(s) restart/rechallenge. Documentation of the informed consent must be recorded in the subject's study chart.
- Study drug(s) must be administered at the dose specified by the GSK Medical Monitor.
- Subjects approved by GSK for restart/rechallenge of study drug(s) must return to the clinic once a week for evaluation of liver chemistry tests until stable liver chemistries have been demonstrated and laboratory monitoring may resume per protocol.
- If protocol-defined stopping criteria for liver chemistry abnormalities are met, study drug(s) administration must stop.

10. CONCOMITANT MEDICATIONS AND NON-DRUG THERAPIES

Subjects will be instructed to inform the investigator prior to starting any new medications from the time of first dose of study treatment until the end of the study (Final Study Visit). Any concomitant medication(s), including non-prescription medication(s) and herbal product(s), taken during the study will be recorded in the electronic case report form (eCRF). Additionally, a complete list of all prior anti-cancer therapies will be recorded in the eCRF.

Concomitant dosing of GSK2857916 with strong Pgp inhibitors should be avoided unless considered medically necessary (See [Appendix 11: Pgp Inhibitors](#) for list of relevant Pgp inhibitors).

If future changes are made to the list of permitted/prohibited medications, formal documentation will be provided by GSK and stored in the study file. The SPM will be updated to include this information. Any such changes will be communicated to the investigative sites in the form of a letter.

10.1. Permitted Medication(s)

Subjects should receive full supportive care during the study, including transfusion of blood and blood products, growth factors, and treatment with antibiotics, anti-emetics, antidiarrheals, and analgesics, as appropriate.

Steroids are not allowed unless used for pre-medication prior to GSK2857916 infusion.

Concomitant therapy with biphosphonates is allowed.

Concomitant prophylactic treatment for tumor lysis syndrome (according to local standards) in subjects with high tumor load, where TLS may occur is permitted and should be considered.

10.2. Prohibited Medication(s)

Chronic treatment with oral steroids is prohibited while the subject is on study.

A short course (up to 7 days) of steroids can be used to manage rash, treatment induced diarrhea, or other acute complications. Steroids may be used to treat infusion related reactions. Inhaled steroids are allowed.

10.3. Permitted Non-Drug Therapies

Subjects may receive local irradiation for pain control or stability control.

10.4. Prohibited Non-Drug Therapies

Plasmapheresis is prohibited from 7 days prior to study entry through the end of study.

11. LIFESTYLE AND/OR DIETARY RESTRICTIONS

11.1. Contraception

11.1.1. Female Subjects

A female of non-childbearing potential (i.e., physiologically incapable of becoming pregnant) is defined as any female who has had a hysterectomy, bilateral oophorectomy (ovariectomy) or bilateral tubal ligation, or is post-menopausal

A practical definition accepts menopause after 1 year without menses with an appropriate clinical profile, e.g., age appropriate, >45 years in the absence of hormone replacement therapy (HRT). In questionable cases, the subject must have a follicular stimulating hormone (FSH) value >40 mIU/mL and an estradiol value < 40pg/mL (<140 pmol/L).

A female of childbearing potential is defined as any female who does not meet the criteria of non-childbearing potential as described in the previous paragraph.

Female subjects of childbearing potential must not become pregnant during the study and so must be sexually inactive by abstinence or use contraceptive methods with a failure rate of <1%.

Abstinence

Sexual inactivity by abstinence must be consistent with the preferred and usual lifestyle of the subject. Periodic abstinence (e.g. calendar, ovulation, symptothermal, post-ovulation methods) and withdrawal are not acceptable methods of contraception.

Complete abstinence from sexual intercourse for 14 days prior to first dose of study treatment, through the dosing period, and for at least 60 days after the last dose of study treatment.

Contraceptive Methods with a Failure Rate of <1%

- Oral contraceptives (either combined or progesterone only) if not contraindicated for this subject population or per local practice.
- Estrogenic vaginal ring if not contraindicated for this subject population or per local practice.
- Percutaneous contraceptive patches if not contraindicated for this subject population or per local practice.
- Implants of levonorgestrel if not contraindicated for this subject population or per local practice.
- Injectable progesterone if not contraindicated for this subject population or per local practice.
- Intrauterine device or intrauterine system that meets the <1% failure rate as stated in the product label

- Male partner sterilization (vasectomy with documentation of azoospermia) prior to the female subject's entry into the study, and this male is the sole partner for that subject. For this definition, “documented” refers to the outcome of the investigator's/designee’s medical examination of the subject or review of the subject's medical history for study eligibility, as obtained via a verbal interview with the subject or from the subject’s medical records.
- Double-barrier method: condom and occlusive cap (diaphragm or cervical/vault caps) plus vaginal spermicidal agent (foam/gel/film/cream/suppository)

These allowed methods of contraception are only effective when used consistently, correctly and in accordance with the product label. The investigator is responsible for ensuring subjects understand how to properly use these methods of contraception.

11.1.2. Male Subjects

To prevent pregnancy in a female partner or to prevent exposure of any partner to the study treatment from a male subject’s semen, male subjects must use one of the following contraceptive methods:

- Abstinence, defined as sexual inactivity consistent with the preferred and usual lifestyle of the subject. Periodic abstinence (e.g. calendar, ovulation, symptothermal, post-ovulation methods) and withdrawal are not acceptable methods of contraception.

Complete abstinence from sexual intercourse from the first dose of study medication, throughout the study treatment period and for at least 60 days after the last dose of study treatment.

- Condom (*during non-vaginal intercourse with any partner - male or female*) **OR**
- Double-barrier method: condom and occlusive cap (diaphragm or cervical/vault caps) plus spermicidal agent (foam/gel/film/cream/suppository) (*during sexual intercourse with a female*)

11.2. Lactation Restrictions

Female subjects who are lactating must discontinue nursing prior to the first dose of study treatment and must refrain from nursing throughout the treatment period and for 4 months following the last dose of study treatment.

12. DATA MANAGEMENT

For this study, data will be collected using defined electronic case report forms (eCRFs), transmitted electronically to GSK and combined with data provided from other sources in a validated data system.

Management of clinical data will be performed in accordance with applicable GSK standards and data cleaning procedures to ensure the integrity of the data, e.g. removing errors and inconsistencies in the data. AEs and concomitant medications terms will be coded using Medical Dictionary for Regulatory Activities (MedDRA) and an internal

validated medication dictionary, GSK Drug. Electronic CRFs (eCRFs), including queries and audit trails, will be retained by GSK, and copies will be sent to the investigator to maintain as the investigator copy.

When laboratory samples (i.e., hematology and clinical chemistry) are analyzed by a central laboratory the results will be stored in a database maintained by the central laboratory and transferred to GSK at agreed times.

In all cases, subject initials will not be collected or transmitted to GSK according to GSK policy.

12.1. Data Dissemination and Communication Plan

The GSK Medical Monitor will review screening packets to ensure that subjects being considered for enrolment meet eligibility criteria prior to entering the study. Subjects will not be assigned a study number until their screening packet is reviewed and approved by the GSK Medical Monitor. GSK will remain in constant contact with the clinical sites during the enrolment period to ensure that cohort enrolment in Parts 1 and 2 of this study are completed as per protocol. Investigators will be informed about available openings for enrolment on the trial and will be asked to pre-screen their subjects to determine potential eligibility, and to avoid over-enrolment. Enrollment will be offered to a given site for a limited period of time, and if the site chosen cannot successfully enrol a subject within a pre-specified time period then another site will be offered the opportunity to enrol a subject.

During Part 1 of the study, Study Team Safety Update Meetings will be held every three weeks to review relevant data with the Principal Investigators (or delegates) and site staff. These meetings will be held on an “as needed” basis (but no less frequent than once a month) during Part 2 (e.g., to share safety experience and to communicate results of scheduled futility analyses). Safety, PK, PD, and clinical outcome data available for all subjects at the time of the scheduled Safety Update Meeting will be reviewed and summarized. In addition, Dose Escalation Meetings will be scheduled at the conclusion of the DLT assessment period for subjects enrolled in each cohort to review safety PK, and PD data and determine the next dose level appropriate for study. Dose escalation decisions will be made with team and investigator agreement after review of available safety data from at least one cycle of therapy with GSK2867916 (i.e., 21 days for the once every 3 weeks schedule and 28 days for weekly schedule). All dose escalation or safety decisions will be documented in writing with copies maintained at each site and the Master Study Files at GSK. Available data will be provided to participants prior to each scheduled Safety or Dose Escalation Meeting.

Attendees of Safety Update and Dose Escalation Meetings will include but not limited to all clinical investigators (or designees) and site staff, the GSK Medical Monitor, Clinical Investigation Lead, Clinical Operations Study Lead (USA and Local Operating Company designees), Data Quality Leader, Global Clinical Safety and Pharmacovigilance Representative, Statistician, CPMS representative, and Translational Medicine Lead.

13. DATA ANALYSIS AND STATISTICAL CONSIDERATIONS

13.1. Hypothesis(es)

13.1.1. Part 1: Dose-Escalation Phase

No formal statistical hypotheses are being tested in Part 1. Analysis of the data obtained from Part 1 will only utilize descriptive methods.

13.1.2. Part 2: Expansion Cohort

For Part 2, hypothesized response rates are provided in Section 13.2.2 below. In this case, a test that the ORR is less than or equal to the null hypothesis rate versus the ORR is greater than or equal to the alternative rate will be performed using the stopping rules provided in Section 13.6.2. Descriptive statistics will be used to describe the observed ORRs at the RP2 dose used in the expanded cohorts.

13.2. Sample Size Determination

The sample size planned for Part 1 arises from the predefined criteria for dose selection and is not driven by statistical considerations. Based on simulations, the anticipated size of Part 1 will be approximately 20 subjects. See Section 13.2.1 and Section 13.2.2 for more details.

The additional 50 subjects in the expanded cohort for Part 2 of the study (which includes approximately 40 MM subjects and approximately 10 subjects with other BCMA positive malignancies) will provide additional safety and tolerability information about the treatment and a better precision around the response rate estimate.

13.2.1. Part 1: Dose-Escalation Phase

The total number of subjects to be enrolled in Part 1 will depend on the number of subjects needed to characterize the individual dose cohorts for determination of the MTD. Simulations were conducted to determine the average sample size and percentage of times each dose was selected under three different scenarios. These scenarios were designed to represent true toxicity profiles which are lower than expected, higher than expected, and in line with expectations. For each scenario, 1000 clinical trials were simulated. Details are provided in Table 16. Doses are the projected doses. Actual doses used during the conduct of the trial may vary.

The specified prior probabilities discussed in Section 3.3.1.2.3 were used to determine an explicit equation for the prior distribution using the FACTS software. The parameters (s.d.) of the explicit distribution are $\alpha=-1.3281$ (1.7153), $\ln(\beta)=-0.795$ (1), and $\rho=-0.9352$ where α and $\ln(\beta)$ are distributed as bivariate normal with correlation ρ .

Table 16 Simulation Results Under Various Scenarios

Dose (mg/kg)	Scenario 1: Below Level of Toxicity		Scenario 2: Expected Level of Toxicity		Scenario 3: Higher Level of Toxicity	
	True DLT Rate	Percent of Trials Selecting Dose as MTD (%)	True DLT Rate	Percent of Trials Selecting Dose as MTD (%)	True DLT Rate	Percent of Trials Selecting Dose as MTD (%)
No Dose		0		0.7		6.8
0.03	0	0	0.001	0	0.05	0.2
0.06	0.01	0	0.02	0	0.075	0.1
0.12	0.025	0	0.05	0.4	0.1	2.6
0.24	0.05	0.1	0.1	1.4	0.15	5.3
0.48	0.075	0.7	0.15	6.7	0.2	20.3
0.96	0.1	4.3	0.2	20.3	0.3	29.0
1.92	0.125	14.1	0.225	30.3	0.35	24.6
2.8	0.15	22.6	0.275	27.9	0.375	9.5
3.6	0.175	22.4	0.35	9.1	0.45	1.2
4.5	0.225	35.8	0.425	3.2	0.55	0.4

The average sample size over the 1000 clinical trials simulated under each of Scenarios 1-3 was 20.55, 20.04, and 19.43 respectively.

13.2.2. Part 2: Expansion Cohort

Dose escalation will be used to establish the RP2 dose for GSK2857916. Once the RP2 dose is confirmed, at least 15 and up to 40 subjects in total will be enrolled into the MM cohort using decision rules defined in [Table 17](#). The sample size and stopping rules are based on the methodology of Lee et al. [[Lee, 2008](#)]. The assumptions underlying the design are detailed below.

The null hypothesis is:

$$H_0: p \leq 20\%$$

The alternative hypothesis is:

$$H_A: p \geq 40\%$$

For the MM expansion cohort, starting with 15 subjects and allowing for a maximum sample size of 40, this design will have a type I error rate (α) of 0.075 and 89.8% power. The trial is not designed to stop early for efficacy, but is designed to stop early for futility if the predictive probability of success is less than 5%. The type I error rate, power, and predictive probability of success to stop early for futility were derived from explicitly stating the minimum and maximum sample size, allowing for the futility stopping rate to range from 5% to 20% within the predictive probability design software, and selection of the optimizing criterion as the maximization of power under the alternative hypothesis. The Bayesian prior probability used in determining the design was Beta (0.25, 0.75), a distribution with a mean response rate of 25%. Under the null hypothesis, if the true response rate is 20%, the expected sample size of the design is 23.4 subjects and probability of early termination (PET) is 88.9%. Under the alternative hypothesis, if the true response rate is 40%, the expected sample size of the design is 38.6 subjects and probability of early termination (PET) is 8.5%.

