13.5. Treatment Comparisons

13.5.1. Primary Comparisons of Interest

No formal hypothesis testing will be performed. Safety, PK, PD markers, and efficacy summaries will be provided by initial dose cohort in Part 1 and by expansion cohort in Part 2.

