13.6. Interim Analysis

13.6.1. Part 1

While no formal interim analysis is planned for Part 1, safety, pharmacokinetic and pharmacodynamic marker data will be examined on an ongoing basis to support dose escalation decisions. Prior to determining the GSK2857916 dose for the next cohort enrolled, exploratory analysis will be conducted to assess the relationship of GSK2857916 dose levels with safety, PK and PD parameters using all data from available cohorts. For more details of the dose escalation procedure, see Section 3.3.

13.6.2. Part 2

The methodology utilized is based on the predictive probability of success if enrollment continues to 40 subjects [Lee, 2008]. The predictive probability design is similar to a Green-Dahlberg design in that it allows for early stopping for futility. The differences are that the predictive probability design allows for evaluation of stopping rules as often as after each subject, rather than at only two stages. While the two designs have similar type I and type II error rates, the probability of early termination is greater with the predictive probability design. In this particular study, we will stop only for futility and evaluate the stopping rules once approximately 15, 22, and 30 subjects are evaluable (though additional futility looks are also controlled for if necessary). A subject is considered evaluable if they are in the all treated population and have had at least two post baseline disease assessments.

For the MM expansion cohort, response data will be reviewed once approximately 15, 22, and 30 subjects are evaluable and the number of overall responses (PR, VGPR, CR, and sCR) observed will be compared with the stopping rules provided in Table 17 below.

Table 17 Futility Stopping Region

Number of Evaluable Subjects	Number of Overall Responses												
	0	1	2	3	4	5	6	7	8	9	10	11	>11
15	Shaded	Shaded	Shaded										
16	Shaded	Shaded	Shaded										
17	Shaded	Shaded	Shaded										
18	Shaded	Shaded	Shaded	Shaded									
19	Shaded	Shaded	Shaded	Shaded									
20	Shaded	Shaded	Shaded	Shaded									
21	Shaded	Shaded	Shaded	Shaded									
22	Shaded	Shaded	Shaded	Shaded	Shaded								
23	Shaded	Shaded	Shaded	Shaded	Shaded								
24	Shaded	Shaded	Shaded	Shaded	Shaded								
25	Shaded	Shaded	Shaded	Shaded	Shaded	Shaded							
26	Shaded	Shaded	Shaded	Shaded	Shaded	Shaded							
27	Shaded	Shaded	Shaded	Shaded	Shaded	Shaded							
28	Shaded	Shaded	Shaded	Shaded	Shaded	Shaded							

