29	Shaded	Shaded	Shaded	Shaded	Shaded	Shaded	Shaded						
30	Shaded	Shaded	Shaded	Shaded	Shaded	Shaded	Shaded						
31	Shaded	Shaded	Shaded	Shaded	Shaded	Shaded	Shaded						
32	Shaded	Shaded	Shaded	Shaded	Shaded	Shaded	Shaded	Shaded					
33	Shaded	Shaded	Shaded	Shaded	Shaded	Shaded	Shaded	Shaded	Shaded				
34	Shaded	Shaded	Shaded	Shaded	Shaded	Shaded	Shaded	Shaded	Shaded	Shaded			
35	Shaded	Shaded	Shaded	Shaded	Shaded	Shaded	Shaded	Shaded	Shaded	Shaded			
36	Shaded	Shaded	Shaded	Shaded	Shaded	Shaded	Shaded	Shaded	Shaded	Shaded			
37	Shaded	Shaded	Shaded	Shaded	Shaded	Shaded	Shaded	Shaded	Shaded	Shaded	Shaded		
38	Shaded	Shaded	Shaded	Shaded	Shaded	Shaded	Shaded	Shaded	Shaded	Shaded	Shaded		
39	Shaded	Shaded	Shaded	Shaded	Shaded	Shaded	Shaded	Shaded	Shaded	Shaded	Shaded	Shaded	
40	Shaded	Shaded	Shaded	Shaded	Shaded	Shaded	Shaded	Shaded	Shaded	Shaded	Shaded	Shaded	Shaded

Note: The shaded regions are the specific regions for stopping the study for futility. For instance, if there are 4-5 or fewer responses in 25 subjects, then the predictive probability for success will be less than the futility criterion, 5.0%, and the study will be stopped.

In addition to the considering the recommendations of the futility analyses, final decisions on stopping enrolment in the MM cohort will depend on the totality of the data collected. Examples of consideration of the totality of the data include, further investigation of the clinical activity of subgroups of subjects based on their BCMA expression levels and evaluation of the quality of responses (including sCR, CR and Clinical Benefit Rate, as defined in [Appendix 1](#)). Should the recommendation to stop for futility be disregarded in favor of a decision to continue the trial based on the totality of the data, the overall type I error rate of the expansion phase will be inflated.

No interim analyses will be performed on the BCMA+ lymphomas cohort; though consideration would be given to closing the cohort should the enrollment be stopped in the MM cohort.

If necessary, a subject may be replaced if they are deemed to be Lost to Follow-Up (LTFU) or they have withdrawn due to a toxicity deemed to not have been related to GSK2857916.

Subjects will not be replaced when they discontinue the study due to: Progression (symptomatic or otherwise), toxicity related to GSK2857916, or lack of efficacy.

Other administrative interim analyses may be performed if needed.

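### The error rates, early-stopping probabilities and expected sizes in protocol 13.2.2 assume a futility check after every subject from 15 to 39, not the planned looks at about 15, 22 and 30

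*Protocol*

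**What the plan says.** Section 13.2.2 sets a null response rate of at most 20% and an alternative of at least 40%. It describes a design "starting with 15 subjects and allowing for a maximum sample size of 40", with no efficacy stop, a futility stop when the predictive probability of success is below 5%, and a Beta(0.25, 0.75) prior. It states that "this design will have a type I error rate (α) of 0.075 and 89.8% power". At 20% response "the expected sample size of the design is 23.4 subjects and probability of early termination (PET) is 88.9" per cent; at 40% the expected size is 38.6 and PET 8.5%. It does not name the look schedule behind these figures.

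Section 13.6.2 says the team will "evaluate the stopping rules once approximately 15, 22, and 30 subjects are evaluable (though additional futility looks are also controlled for if necessary". The synopsis and sections 3.1 and 3.4 give the same three looks. Section 13.6.2 also says that "final decisions on stopping enrolment in the MM cohort will depend on the totality of the data collected", and that disregarding a futility recommendation would inflate the type I error rate. It does not say by how much.

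Table 17 has a row for every number of evaluable subjects from 15 to 40. Its note gives 4-5 or fewer responses in 25 as an example of stopping. Section 13.1.2 says the response rate will be tested using these rules, whereas section 13.5.1 says "No formal hypothesis testing will be performed".

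**The concern.** Type I error, power, PET and expected size all depend on how often the futility rule is applied. Dropping binding futility looks lets more trials run to 40 subjects. Under the null this lowers PET and raises both expected size and type I error. If the printed figures belong to a denser schedule than the one planned, section 13.2.2 tells its reader that an inactive regimen will be stopped early more often than it will be. The protocol prints these numbers as properties of its own design, so the matter cannot be left to a later analysis plan.

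**Working it through.** **Inputs (13.2.2 and 13.6.2).** p0 = 0.20; p1 = 0.40; first look at n = 15; maximum N = 40; prior Beta(0.25, 0.75); stop if predictive probability < 5%; no efficacy stop; planned looks 15, 22, 30.

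**Success rule.** The text does not state it. Success at r = 12 or more of 40 is inferred from the last column of Table 17 (more than 11). It is confirmed because it reproduces the stated figures, while thresholds of 11 and 13 do not.

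**Boundary.** With x responses in n subjects, the remaining responses Y follow a beta-binomial(40 − n, 0.25 + x, 0.75 + n − x), and PP(x, n) = P(Y ≥ 12 − x). The boundary at n is the largest x with PP < 0.05:

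- n = 15: PP(2) = 3.2%, PP(3) = 14.3%, so stop at 2 or fewer.
- n = 22: PP(4) = 4.2%, PP(5) = 15.5%, so stop at 4 or fewer.
- n = 25: PP(5) = 4.99%, PP(6) = 17.6%, so stop at 5 or fewer.
- n = 30: PP(6) = 1.7%, PP(7) = 8.8%, so stop at 6 or fewer.

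These agree with Table 17. Rows 33 to 40 of that table as extracted look shifted by about one cell. That may be an artefact of reading the PDF, and those rows do not enter the three-look result.

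**Operating characteristics.** The response count is carried forward one subject at a time by exact binomial recursion. Probability at or below the boundary is removed at each look. Then PET = sum of stop probabilities, E[N] = Σ n·P(stop at n) + 40·(1 − PET), and the rejection probability = P(not stopped and at least 12 responses).

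| Quantity | Stated | Every subject, 15–39 | Looks at 15, 22, 30 | Never stopped |
|---|---|---|---|---|
| Type I error | 0.075 | 0.0754 | 0.0799 | 0.0875 |
| Power | 89.8% | 89.75% | 90.8% | 92.9% |
| PET at 20% | 88.9% | 88.85% | 68.3% | 0 |
| E[N] at 20% | 23.4 | 23.42 | 25.73 | 40 |
| PET at 40% | 8.5% | 8.49% | 4.6% | 0 |
| E[N] at 40% | 38.6 | 38.64 | 39.02 | 40 |

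The every-subject column matches all six stated figures to printed precision. No three-look variant tried does so.

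**Hand check of the three-look column at 20%.** Stop probabilities are 0.398 at 15, 0.184 at 22 and 0.102 at 30, which sum to 0.683 after rounding. E[N] = 15 × 0.398 + 22 × 0.184 + 30 × 0.102 + 40 × 0.317 ≈ 25.7.

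**Where the PET gap lies.** 88.9 − 68.3 = 20.6 points. Checking after every subject from 15 to 30 and then no more gives PET 72.4%. So about 72.4 − 68.3 = 4 points of the gap arise by subject 30, and about 88.9 − 72.4 = 16 points are stops at 31 to 39. Expected size differs by 25.7 − 23.4 = 2.3 subjects.

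**Approximate timing.** Moving the three looks over 15–17, 20–24 and 28–32 gives type I error 0.079–0.085, power 90.7–92.2%, PET at 20% of 55–75% and E[N] at 20% of 25.4–29.3. No combination reaches 0.075 or 88.9%.

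**The case against.** The figures are arithmetically right for a rule applied at every row of Table 17. Section 13.2.2 refers to that table, and section 13.6.2 says the method allows evaluation after each subject, so the basis is partly disclosed. That stands: this is a mismatch between the quoted design and the planned conduct, not a slip in calculation. It does not remove the mismatch, because every description of the planned looks names only three.

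Three stronger readings are tempting and should be resisted.

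- A reader might infer that the remark about additional looks being controlled for is backwards. It is not. Extra binding futility looks take type I error from 0.080 down to 0.075, so the remark is true. It simply does not cover using fewer looks than the figures assume.
- A reader might infer that the possible override is concealed. Section 13.6.2 says openly that disregarding a futility recommendation inflates type I error. Only its size is missing.
- A reader might take the 21-point PET gap as a measure of subjects needlessly treated. Most of it is stopping after subject 30, when few subjects remain to be spared.

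It is also fair that the overall response rate is a secondary endpoint in a Phase I study, that power is not harmed, and that exact values for looks timed only approximately would be falsely precise without a range.

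**Conclusion.** The point holds as a misstatement of design properties. For the looks in section 13.6.2, PET at a 20% response rate is 68.3% (55–75% for nearby timings) rather than 88.9%. The chance that a regimen with a 20% response rate runs to 40 subjects is therefore about 32% (100 − 68.3), not 11% (100 − 88.9). Type I error is 0.080 (0.079–0.085) rather than 0.075, and expected size at 20% is 25.7 (25.4–29.3) rather than 23.4. Power is 90.8%, about one point above the stated value. PET is the material discrepancy; the rest are small. The documents do not support a claim that error control is lost: even if no futility stop is acted on, type I error is at most 0.0875, with power 92.9%.

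These results assume success at 12 or more of 40, exactly binomial responses, and binding stops at the looks used except in the never-stopped case.

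**What to change.** In section 13.2.2, do one of two things:

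1. Restate the figures for looks at 15, 22 and 30: type I error 0.080, power 90.8%, PET 68.3% and 4.6%, expected size 25.7 and 39.0. Add the range above for approximate timing.
2. Keep the present figures, commit in section 13.6.2 to applying the rule after every evaluable subject from 15, and say that the figures assume this.

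In either case:

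- Add to the existing caveat in section 13.6.2 that type I error is at most 0.0875 (power 92.9%) if futility stops are not acted on.
- State in words that success means at least 12 responses in 40.
- Reconcile section 13.1.2, which announces a test, with section 13.5.1, which denies one.
- Change the Table 17 note to 5 or fewer responses in 25.

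The first option is a text change that needs no change to the planned looks or the maximum of 40, though some printed figures become less favourable. The second keeps the figures but requires response review after each evaluable subject.
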